**Table 7. Time Schedule – Day 2 Washout**

Time	Blood sample	Procedures	Additional information
Start of procedure			
		Nicotine abstinence	All day
		Support during nicotine abstinence as required	All day
		AE/SAE recording, concomitant medication	All day
	√	Plasma nicotine PK sample	24 hrs +5 min after T 0 of Day 1
		Assessment of cough	24 hrs minus 5 min after T 0 of Day 1
7:30 AM-10:00 AM		Breakfast	
8:00 AM-9:30 AM		CO breath test	
10:00 AM-11:30 AM		Vital signs	At least 5 min in supine position prior to measurement
12:00 PM-1:30 PM		CO breath test	
1:00 PM-2:30 PM		Lunch	
4:00 PM-5:30 PM		CO breath test	
4:30 PM-5:00 PM		Snacks	
6:30 PM-9:00 PM		Dinner	
8:00 PM-9:30 PM		CO breath test	

Abbreviations: AE = Adverse event; CO = Carbon monoxide; PK = Pharmacokinetic; SAE = Serious adverse event; T = Time point.

Confidentiality Statement: Data and information contained in this document are considered to constitute trade secrets and confidential commercial information, and the legal protections provided to such trade secrets and confidential information are hereby claimed under the applicable provisions of applicable law. No part of this document may be publicly disclosed without the written consent of Philip Morris Products SA.

### 9.3.2 Days of Single Use (Day 1 and Day 3)

On the days of single use (Day 1 and Day 3) the following assessments will be performed (Table 8):

**Table 8. Time Schedule – Day 1 and Day 3 Single Use**

Time	Blood sample	Procedures	Additional information
Start of procedure			
		Optional: light snacks prior first blood draw of the day	
		AE/SAE recording, concomitant medication	All day
		Support as required	All day
		Craving questionnaire (QSU-brief)	First time prior to T0, then 15 min +5 min, 30 min +5 min, 45 min +5 min, 1 hr +5 min, 2 hrs +5 min, after T0, then and 4 hrs +10 min, 6 hrs +10 min, 9 hrs +10 min, and 12 hrs +10 min
√		Plasma nicotine sample	First sample within 15 min prior to T0, 15 samples thereafter in relation to T0: T1 after 2 min +1 min, T2 after 4 min +1 min, T3 after 6 min +1 min, T4 after 8 min +1 min, T5 after 10 min +1 min, T6 after 15 min +2 min, T7 after 30 min +2 min, T8 after 45 min +2 min, T9 after 60 min +3 min, T10 after 2 hrs +5 min, T11 after 4 hrs +5 min, T12 after 6 hrs +5 min, T13 after 9 hrs +5 min, T14 after 12 hrs +5 min, and T15 after 24 hrs +5 min)
√		COHb blood sampling	Five blood samples to be taken, first sample within 15 min prior to T0, then after 15 min +2 min, 60 min +3 min, 4 hrs +5 min, 12 hrs +5 min
		CO breath test	First test to be done within 15 min prior to T0
		Assessment of cough	Has to be done prior to product use

Confidentiality Statement: Data and information contained in this document are considered to constitute trade secrets and confidential commercial information, and the legal protections provided to such trade secrets and confidential information are hereby claimed under the applicable provisions of applicable law. No part of this document may be publicly disclosed without the written consent of Philip Morris Products SA.

6:00 AM-9:00 AM	Start of single product use	
7:30 AM-10:00 AM	Breakfast	
10:00 AM-11:30 AM	Vital signs	At least 5 min in supine position prior to measurement
10:00 AM-11:30 AM	ECG	At least 10 min in supine position prior to recording
12:00 PM-1:30 PM	CO breath test	
1:00 PM-2:30 PM	Lunch	
4:00 PM-5:30 PM	CO breath test	
5:00 PM-5:30 PM	Snacks	
6:30 PM-9:00 PM	Dinner	
8:00 PM-9:30 PM	CO breath test	
8:00 PM-11:00 PM	Product evaluation questionnaire (MCEQ; only in sequence 1 and 2)	
	Collection of used Tobacco Sticks and CC butts and NNS	After the product use

Abbreviations: AE = Adverse event; CC = conventional cigarette(s); CO = Carbon monoxide; COHb = Carboxyhemoglobin; ECG = Electrocardiogram; MCEQ = Modified Cigarette Evaluation Questionnaire; NNS = nicotine nasal spray; QSU-brief = Questionnaire of Smoking Urges; SAE = Serious adverse event; T = Time point;

Confidentiality Statement: Data and information contained in this document are considered to constitute trade secrets and confidential commercial information, and the legal protections provided to such trade secrets and confidential information are hereby claimed under the applicable provisions of applicable law. No part of this document may be publicly disclosed without the written consent of Philip Morris Products SA.

## 9.4 Day of Discharge

The following assessments will be conducted prior to the time of Discharge on Day 4 (or after a subject is prematurely withdrawn from the study) ([Table 9](#)):

**Table 9. Time Schedule – Day 4 Discharge**

Time	Blood sample	Procedures	Additional information
Start of procedure			
		AE/SAE recording, concomitant medication	All day
	√	Plasma nicotine: PK sample	24 hrs since $T_0$ of Day 3 +5 min
		Assessment of cough	24 hrs since $T_0$ of Day 3 minus 5 min
7:30 AM-9:00 AM	√	Clinical laboratory parameters (haematology, urine analysis, clinical chemistry)	
7:30 AM-9:00 AM		Urine pregnancy test	
9:00 AM-10:00 AM		Breakfast	
10:00 AM-11:30 AM		Vital signs	At least 5 min in supine position prior to measurement
10:00 AM-11:30 AM		CO breath test	
10:00 AM-11:30 AM		Spirometry	
10:00 AM-11:30 AM		Physical examination, weight and calculated BMI	
10:00 AM-11:30 AM		Advice on risk of smoking and debriefing	
10:00 AM-11:30 AM		Time of discharge	

Abbreviations: AE = Adverse event; BMI = Body mass index; CO = Carbon monoxide; PK = Pharmacokinetic; SAE = Serious adverse event; T = Time point

Smoking will be allowed after spirometry has been conducted.

Confidentiality Statement: Data and information contained in this document are considered to constitute trade secrets and confidential commercial information, and the legal protections provided to such trade secrets and confidential information are hereby claimed under the applicable provisions of applicable law. No part of this document may be publicly disclosed without the written consent of Philip Morris Products SA.

## 9.5 Safety Follow-up Period

After the time of Discharge at Day 4 (or if prematurely withdrawn from the study), subjects will enter a 7-day safety follow-up period.

During the 7-day safety follow-up period, there will be spontaneous reporting by the subject of new AEs and new SAEs. Any ongoing AEs/SAEs will be actively followed up by the site.

Any AEs or SAEs that are ongoing at the end of the 7-day safety follow-up period will be handled as described in [Section 8.2.2](#).

## 9.6 Early Termination Procedures

The Day of Discharge assessments will be performed as early termination procedures (see [Section 9.4](#)). Early termination procedures will be the same as those described in the day of Discharge.

## 10 QUALITY CONTROL AND QUALITY ASSURANCE

### 10.1 Monitoring

A Clinical Research Associate (“Monitor”) from an independent CRO not involved with the study site will be responsible for the monitoring of the study. Monitoring will be performed according to the study CRO’s SOPs and as per the agreed monitoring plan with the Sponsor.

The Investigator shall permit the Monitor to review study data as frequently as deemed necessary to ensure that data are being recorded in an adequate manner and that protocol adherence is satisfactory.

The Investigator shall access medical records for the Monitor so that entries in the eCRFs may be verified. The Investigator, as part of their responsibilities, is expected to ensure that the study adheres to GCP requirements.

An Investigator’s meeting will be held prior to the site initiation visit. During this meeting, the general training of the study procedures and specific training on selected procedures will be performed and documented.

Subsequent to the Investigator’s meeting, and before the first subject is screened, the site initiation visit will be conducted by the Monitor and, if necessary, with the Sponsor or its authorized representative. The purpose of the site initiation visit is detailed in the monitoring plan.

Communication by telephone, mail, and e-mail may be used as needed to supplement site visits. The Investigator and study personnel will cooperate with the Monitor, provide all appropriate documentation, and will be available to discuss the study.

The Monitor and the Sponsor’s personnel will be available between visits, should the Investigator or other staff at the sites need information and advice.

Site visits will be made at regular intervals during the study. The frequency of the monitoring visits will be defined in the monitoring plan agreed with the Sponsor.

The Investigator, or a designated member of the Investigator’s staff, must be available during the monitoring visit to review the data and resolve any queries, and to allow direct access to the subject’s records for source data verification.

## 10.2 Training of Staff

A formal meeting (Investigator's meeting) will be conducted prior to site initiation. During this meeting, the Sponsor or its authorized representative will discuss the requirements of the clinical study protocol and related documents and will also provide training in the relevant systems and other study-specific procedures. The activities of the Investigator's meeting will be described in the monitoring plan.

In addition to the Investigator's meeting, the Principal Investigator will ensure that appropriate training relevant to the study is provided to all staff involved in the study, and that any new information relevant to the performance of this study is forwarded to the staff involved in a timely manner. The Principal Investigator will maintain a record of all individuals involved in the study.

## 10.3 Audits and Inspections

GCP regulations require that there are independent inspections of clinical program activities. Such inspections may be performed at any time before, during, and/or after the study.

Authorized representatives of the Sponsor, regulatory agencies and/or an IEC may perform audits or inspections, including source data verification. The purpose of an audit or inspection is to systematically and independently examine all study-related activities and documents to determine whether these activities were conducted, and data were recorded, analysed, and accurately reported according to the protocol, ICH/GCP guidelines, and any applicable regulatory requirements. The Investigator will contact the Sponsor or the authorized representative immediately, if contacted by a regulatory agency about an inspection at their site.

The Investigator and study staff are responsible for maintaining a comprehensive and accurate filing system of all study-related documentation that will be suitable for inspection at any time by the Sponsor, its authorized representative, and/or regulatory agencies. In signing this protocol, the Investigator understands and agrees to provide access to the necessary documentation and files.

## 11 DATA MANAGEMENT ACTIVITIES

All Data Management Activities will be described in detail in the Data Management Plan and documents specified therein.

### 11.1 Data Capture

#### 11.1.1 Case Report Forms and Study Records

With the exception of the subject-reported outcome data, all results from the clinical assessments will be recorded in the Source Documents by the Investigator or their authorized designee(s) and then captured in the eCRFs at the study site. The subject questionnaires and the VAS will be entered by the subject directly in the electronic patient-reported outcomes device or in paper copies. Trained study personnel will be responsible for capturing the data from the observations, tests and assessments specified in the protocol in the source documents and then transferring the data into the eCRF, in accordance with the Case Report Form Completion Guidelines.

The Investigator has ultimate responsibility for the collection and reporting of all data related to the clinical study and ensuring that the data are accurate, authentic/original, legible, timely (contemporaneous), enduring and available when required. The eCRF must be signed by the Investigator to attest that the data contained in the eCRF are true and accurate. Any corrections made to source documents must be clearly recorded, without obscuring the original values and be accompanied by the date of change, reason for change and identification of the person making the change. The eCRF for each subject will be checked against the source documents at the study site by the Clinical Research Associate. Instances of missing or unclear data will be discussed with the Investigator for resolution. An eCRF will be generated for all subjects that sign the informed consent form.

#### 11.1.1 Protocol Deviations

Protocol deviations are defined as those deviations from any procedure as defined in this document, including but not limited to, as any violation of inclusion/exclusion criteria, mis-randomizations, use of any nicotine or tobacco-containing product other than the assigned product during each of the exposure period, use of any nicotine tobacco-containing product during wash-out days, assessments not performed or performed outside the scheduled time windows, or use of oestrogen or other drugs that are known to affect CYP2A6 activity.

All protocol deviations will be entered into the Clinical Trial Management System (CTMS) or other approved format.

Confidentiality Statement: Data and information contained in this document are considered to constitute trade secrets and confidential commercial information, and the legal protections provided to such trade secrets and confidential information are hereby claimed under the applicable provisions of applicable law. No part of this document may be publicly disclosed without the written consent of Philip Morris Products SA.

Information from the source documents will represent the primary source of protocol deviations. Information following site monitoring and other manual reviews will be documented in the site visit reports, follow-up letters, audit documentation, or other manual review and will be recorded and tracked in the CTMS or other approved format. Telecommunications and other verbal communications regarding deviations will be considered and handled as important communication, documented and tracked as protocol deviations, as necessary.

Individual entries for protocol deviations that are recorded in the CTMS, or other approved format, following site monitoring and other manual reviews, will be reviewed against the individual data points in the eCRF database but will not be formally reconciled with the eCRF database (e.g., their description or occurrence date). The overall procedure for managing protocol deviations are described in the SOPs of the CRO Data Management Team. All deviations will be reviewed periodically, as determined at study start, to identify trends to improve monitoring and/or potential impact on the statistical analysis.

## 11.2 Data Handling

All study data will be managed by the Data Management Team at the CRO. The overall procedures for quality assurance of clinical study data are described in the SOPs of the CRO Data Management Team. The Data Management Team at the CRO will prepare a Data Management Plan, to be reviewed and approved by the Sponsor, prior to the start of the study. This document will describe, in detail, the procedures and processes related to Data Management.

All data of all subjects successfully enrolled, as well as subjects who failed screening, and/or experienced an AE during the study (from time of signing the informed consent form to the end of the safety follow-up period), will be captured and stored in the study database.

All data collected during the study is property of the Sponsor, irrespective of the location of the database and the Data Management CRO.

### 11.2.1 Data Validation

The data will be validated as defined in the Data Management Plan and Data Validation Specifications. Discrepancy lists will be generated electronically, as necessary.

Data queries will be raised for discrepant or missing data. All changes to data will be captured in the database with a comprehensive audit trail.

Confidentiality Statement: Data and information contained in this document are considered to constitute trade secrets and confidential commercial information, and the legal protections provided to such trade secrets and confidential information are hereby claimed under the applicable provisions of applicable law. No part of this document may be publicly disclosed without the written consent of Philip Morris Products SA.

### 11.2.2 Coding

Adverse events, medical/surgical history, and prior/concomitant medication will be classified according to the terminology of the latest version of the following Dictionaries, at time of coding the first entry:

Medical history: Medical Dictionary for Regulatory Activities (MedDRA®)

Adverse events: MedDRA®

Medications: WHO Drug Dictionary Enhanced and Anatomical Therapeutic and Chemical classification system

THS 2.2 device issues and/or malfunctions: C54451/Medical\_Device\_Problem\_Codes\_FDA\_CDRH ([FDA, 2012b](#))

### 11.2.3 Database Lock

When all outstanding Data Management issues have been resolved and all validation, quality review and cleaning activities are complete, the database or selected data is/are declared soft-locked. Access to change data in the soft-locked database or to change selected data at this time is limited.

After data review by the Sponsor, resolution of all raised queries and QC of the changed data, the database or selected data thereof will be declared locked upon Sponsor approval, as applicable.

Any changes to the database after that time can only be made by written agreement between the Sponsor and the Data Management and Statistical Team at the CRO. Any of those changes must be documented in the database log file.

After study completion, the study database will be transferred to the Sponsor in the format specified in the Data Management Plan in the Clinical Data Interchange Standards Consortium Study Data Tabulation Model Data Structure Specifications.

## 12 PLANNED STATISTICAL METHODS

### 12.1 General Considerations

An incomplete block design will be adopted in this study with every subject being exposed to 2 out of the 3 study products(CC, THS 2.2, and NNS) to allow comparisons between THS 2.2 and CC in Group-1 (sequence 1 and 2), and between THS 2.2 and NNS in Group-2 (sequence 3 and 4).

Full details of the statistical analysis will be given in a SAP. Any changes to the planned statistical methods will be documented in the Clinical Study Report. The statistical evaluation will be performed using SAS®, version 9.2 or later.

#### 12.1.1 Stratification Criteria

For analysis, the following stratification criteria will be used:

- Sex (male and female)
- CC nicotine level at Admission (ISO nicotine levels  $\leq 0.6$  mg and  $> 0.6 \leq 1$  mg)

In addition, for the safety data, the analysis will be stratified by sequence and by study periods (Screening, product test, product exposure, and safety follow-up period).

#### 12.1.2 Definitions for Statistical Data Analysis

Unless otherwise stated, for the purposes of statistical analyses, baseline is defined as the last available time point prior to  $T_0$  on Day 1, from 6:00 AM to 9:00 AM.

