### **6.2.2 Investigational Period (Day 0 to Day 3)**

During the first washout, each subject will maintain nicotine abstinence from Day -1 at 11:00 PM to the time of single use of his/her allocated product at Day 1. At Day 1, after the single use of the product, subjects will maintain nicotine abstinence for the rest of the day. During the second washout on Day 2, subjects will maintain nicotine abstinence until the time of single use of subject's allocated product at Day 3. Subjects will not be allowed to smoke or use any other nicotine/tobacco-containing products other than the products they are allocated to.

**Confidentiality Statement:** Data and information contained in this document are considered to constitute trade secrets and confidential commercial information, and the legal protections provided to such trade secrets and confidential information are hereby claimed under the applicable provisions of applicable law. No part of this document may be publicly disclosed without the written consent of Philip Morris Products SA.

Time point of first product use during study day ( $T_0$ ) will be defined as start of the single product use at the single use days. The start of product use for THS 2.2 is defined as the time of the first puff. The start time for CC corresponds to the lighting of the CC, and the start time of the product is the time of the spray in the first nostril. The 30 seconds it takes to pre-heat the Holder will not be taken into account. **The subject must not take a puff of the Tobacco Stick during the pre-heating time.**

The start of the first product use can be different for each subject both days of product use; however, it must be in the window of 6:00 am to 9:00 am.

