#### 7.4.9 Vital Signs

Systolic and diastolic blood pressure, pulse rate, and respiratory rate will be measured at the Screening Visit, at Admission, and at every day in confinement. All parameters will be recorded in supine position after the subject has rested for at least 5 minutes.

For every measurement it has to be documented if the subject has smoked within 15 minutes prior to the measurement.

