#### 12.6.5 Safety Endpoints

In general, all safety data will be listed and tabulated on the safety population by sequence, using the approach described in [Section 12.1.3](#). Safety variables collected during exposure periods will also be reported by product exposure.

AEdatas will serve as the primary assessment of safety. Other safety variables monitored in this study include: respiratory symptoms (cough assessment VAS and Likert scales); vital signs (systolic and diastolic blood pressure, pulse rate, respiratory rate); spirometry; ECG data; clinical chemistry, haematology, and urine analysis safety panel; physical examination; and concomitant medication.

The number and percentage of subjects with AEs and SAEs will be tabulated by system organ class and preferred term. Summaries will also be presented for AEs leading to withdrawal, AEs leading to Death, AEs by relatedness to product exposure, AEs by severity, and laboratory AEs. Tabulations will be performed for both the number of subjects experiencing an event and the number of events. The number and percentage of device events and of subjects with device events will be tabulated by sequence.

Confidentiality Statement: Data and information contained in this document are considered to constitute trade secrets and confidential commercial information, and the legal protections provided to such trade secrets and confidential information are hereby claimed under the applicable provisions of applicable law. No part of this document may be publicly disclosed without the written consent of Philip Morris Products SA.

The number and percentage of subjects with clinical findings will be tabulated by sequence for laboratory parameters. Shift tables showing change from baseline of clinical findings will be provided for ECGs, physical examinations, and laboratory parameters (both shifts in normal ranges and toxicity grades). Descriptive statistics will be summarized by visit and change from baseline for laboratory parameters, ECG, respiratory symptoms, and vital signs.

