#### 7.4.10.2 Electrocardiogram

An ECG will be recorded at Screening and on the following study days: Day 1 and Day 3. The ECG testing will be performed as per the site local practice. A standard 12-lead ECG will be recorded after the subject has rested for at least 10 minutes in supine position.

The following parameters will be documented: heart rate, PR interval, QRS interval, QT interval and QTc interval, corrected by the ECG device according to Bazett's formula. Every ECG has to be assessed as normal, abnormal – clinically not relevant, or abnormal – clinically relevant. A diagnosis has to be provided in the eCRF for all ECGs assessed as abnormal – clinically relevant. ECG print-outs will be interpreted by a qualified physician. Any print-outs of ECGs on thermo-sensitive paper must be photocopied, initialled, dated, and stapled together for inclusion in the Source Data File.

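### One pre-Day 1 baseline for both crossover periods, with clock-timed ECG and vital signs, makes per-product safety changes mix the product effect with abstinence and an uneven lag after use

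*Protocol*

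**What the plan says.** Protocol section 12.1.2 gives a default that applies unless something else is stated: "baseline is defined as the last available time point prior to" T0 on Day 1, with a clock window of 6:00 to 9:00 AM attached. No baseline is defined for Period 2.

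Section 12.6.5 describes the tables: "Descriptive statistics will be summarized by visit and change from baseline for laboratory parameters, ECG, respiratory symptoms, and vital signs". It adds shift tables for ECG, physical examination and laboratory values, and says "Safety variables collected during exposure periods will also be reported by product exposure". Adverse events are the primary safety assessment.

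The schedule behind these tables is:

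- **ECG** (section 7.4.10.2): "An ECG will be recorded at Screening and on the following study days: Day 1 and Day 3". Table 8 places both in-study ECGs at "10:00 AM-11:30 AM". Its only timing note is "At least 10 min in supine position prior to recording"; there is no link to T0.
- **Vital signs** (section 7.4.9): these "will be measured at the Screening Visit, at Admission, and at every day in confinement". Tables 6 to 8 use the same clock window on Days 0 to 3.
- **Cough** (section 7.8.2, Table 8): daily from Day 0 to Day 4, and before product use on Days 1 and 3.
- **T0** (section 6.2.2): it may differ between subjects and between one subject's two days, but "it must be in the window of 6:00 am to 9:00 am".

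Table 8 and section 12 appear only in the first protocol version. The amended version repeats the ECG and vital-sign days, but the supplied text of it stops in section 7.

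**The concern.** Each subject uses two products on two days, and the safety tables are meant to be read by product. A change can be read that way only if it starts from a reference close to that product's use and ends at a comparable time after it. The stated rules secure neither.

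The reference is the same for both periods and lies before the first product, so a Period 2 change covers two further days, almost all of them without nicotine. For the ECG it is a Screening value from a time when subjects smoked by habit (section 6.2). Abstinence can itself move what is measured: Appendix 4 lists a lower heart rate among withdrawal symptoms, and section 7.4.10.2 records heart rate and a Bazett-corrected QTc, which depends on heart rate.

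The end point is set by the clock, so the time since use varies between subjects and between a subject's two days. At stake is whether the per-product ECG, vital-sign and cough changes can be interpreted.

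**Working it through.** **Inputs.** Smoking ends at 11:00 PM on Day -1 (section 6.2.2). T0 is 6:00 to 9:00 AM on Days 1 and 3. ECG and vital signs are at 10:00 to 11:30 AM (Table 8). The nicotine half-life is about 2 h, and the wash-out is at least 24 h, stated as more than 5 half-lives (section 4.2).

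**1. The plan's own figure.** 24 h / 2 h = 12 half-lives, which is more than 5. The statement holds.

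**2. Which value becomes the baseline.**

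- ECG: no ECG precedes T0 on Day 1 except Screening (Day -29 to Day -2), which is 3 to 30 days before Day 1.
- Vital signs: the last value before Day 1 T0 is Day 0, 10:00 to 11:30 AM, 11 to 12.5 h after smoking ended.
- Cough: the Day 1 pre-use value.

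All three then serve for Day 3 (and, for cough, Day 4) as well, although pre-use Period 2 values exist: Day 2 vital signs and Day 3 pre-use cough.

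**3. Abstinence.** From 11:00 PM on Day -1 to Day 1 T0 is 31 to 34 h. To Day 3 T0 it is 79 to 82 h, interrupted only by the single Day 1 use.

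**4. Lag after use.** Fraction remaining = 2^(-lag / 2 h).

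| T0 | Reading | Lag | Remaining |
|---|---|---|---|
| 9:00 | 10:00 | 1.0 h | 2^(-0.5) = 0.71 |
| 6:00 | 11:30 | 5.5 h | 2^(-2.75) = 0.15 |
| 9:00 | 11:30 | 2.5 h | 2^(-1.25) = 0.42 |
| 6:00 | 10:00 | 4.0 h | 2^(-2) = 0.25 |

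The first two rows are the extremes, a ratio of about 4.8. The last two apply if subjects are read in the order in which they started (an assumption); the ratio is then about 1.7.

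**5. Carry-over.** Day 1 T0 to Day 3 T0 is 45 to 51 h, or 22.5 to 25.5 half-lives. The fraction left is at most 2^(-22.5), about 2 in 10 million.

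**6. Effect on the product comparison.** With one shared baseline B, (Day 1 - B) - (Day 3 - B) = Day 1 - Day 3, so B drops out within each subject. For drift, suppose -6 units in Period 1 and -8 in Period 2 (illustrative values, not from the documents):

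- With 22 and 22 per sequence, each product's mean change includes (22 x -6 + 22 x -8) / 44 = -7. The difference between products is 0. The same holds for 9 and 9.
- With assumed dropout to 22 and 18, the means are -6.9 and -7.1, a difference of 0.2. With 9 and 7 they are -6.875 and -7.125, a difference of 0.25.

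The -7 stays in each product's own change, and very little reaches the difference.

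**7. The time window.** Read as describing T0, the 6:00 to 9:00 AM in section 12.1.2 agrees with section 6.2.2. Read as limiting the baseline measurement, it would leave ECG and vital signs with no baseline.

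**The case against.** The strongest reply has five parts.

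- **The readings do follow the product.** On Days 1 and 3, ECG and vital signs come 1.0 to 5.5 h after that day's use. A reader might infer that the tables show abstinence or the other product in place of the one used, or that the ECGs are taken after at least 31 h without nicotine. Neither is supported: the 31 to 34 h end at T0, on Day 1 no other allocated product has been used, and by Day 3 the first is more than 22 half-lives gone. This stands.
- **The product comparison is largely safe.** Shared baseline and balanced drift cancel in it. This stands, but section 12.6.5 plans per-product changes and shift tables, where they do not cancel. Nor does the cancellation cover a lag that differs between a subject's two days.
- **The SAP may override the default.** True for the baseline, which section 12.1.2 leaves open to other definitions. It does not cover the clock schedule, which is set in the protocol.
- **A same-period baseline is not clean either.** For vital signs, Day 0 is 11 to 12.5 h into abstinence. Day 2 is 59 to 60.5 h after usual smoking ended and 25 to 29.5 h after the Day 1 product. Section 12.6.3 itself declines to adjust QSU-brief for the pre-T0 value. This stands as a limit on the remedy.
- **The 4.8-fold range is a corner case.** Section 9 says listed times are for the first subject, with windows for the rest, so 1.7-fold is plausible. This stands.

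**Conclusion.** The point holds as a minor one. As written, per-product changes and ECG shifts combine the product effect with abstinence drift: the ECG is set against usual smoking at Screening, and Day 3 vital signs and Day 3 and 4 cough against values from before the Day 1 product. The lag after use runs from 1.0 h to at most 5.5 h, about 71% to 15% of nicotine remaining by simple decay at the protocol's 2-h half-life, and may differ between a subject's two periods.

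A reader might go further and infer a biased product comparison or carry-over of the first product. The documents support neither. The PK endpoints are unaffected, and only descriptive safety tables are touched.

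The documents give no expected ECG or vital-sign effect, so the distortion cannot be stated in clinical units. The conclusion also assumes that Table 8 and section 12 are unchanged in the amended version. The amendment document supplied alters only the socio-economic questionnaire, but the two protocol versions differ elsewhere too, so this needs checking.

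**What to change.** - **(a)** Schedule the existing Day 1 and Day 3 ECG and vital signs at one fixed interval after T0, the same on both days. No procedure is added; the cost is staggered scheduling at the site.
- **(b)** Where pre-use values exist in both periods (cough before use on Days 1 and 3, vital signs on Days 0 and 2), take the last value before T0 of the same period as baseline for by-product changes. Note beside the table that the vital-sign baselines still differ in length of abstinence.
- **(c)** For ECG, present the within-subject product difference (Day 1 against Day 3) beside the shift from Screening, and label the latter as including abstinence.
- **(d)** State in section 12.1.2 whether 6:00 to 9:00 AM describes T0 or restricts the baseline measurement.

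Items (b) to (d) are wording changes that use data already planned. Sample size, power and error rates do not change.
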